7.9 Subgroup Analyses

Efficacy analyses specified for the Full Analysis Set for phase 3 will be repeated within the following subgroups:

- PD-L1 status (positive, not positive) at baseline
- Disease stage (less advanced [stage IIIB/C-IVM1a], more advanced [stage IVM1b/c]) at baseline (IVRS)
- Prior treatment with BRAF inhibitor (IVRS)
- Region, if applicable (USA or non-USA)
- Age: < 65, ≥ 65; < 75, ≥ 75 years
- LDH: ≤ ULN vs > ULN
- Sex (female vs male)
- ECOG performance status (0 vs 1)
- HSV-1 serostatus (positive vs negative vs missing/unknown)
- The sum of longest, or shortest for nodal, diameters of baseline target lesions (SLD) determined by BICR (**≤ median of SLD vs > median of SLD**)
- Baseline *BRAF*^{V600} mutation (yes vs no vs missing/unknown)

The sum of longest, or shortest for nodal, diameters of baseline target lesions (SLD) will be dichotomized into two groups based on the median calculated at the time of analysis.

[figure not shown]
These subgroups will be re-examined for appropriateness and may be re-categorized or omitted (due to small sample size, for example, if there are < 10% of subjects within a subgroup) before unblinding. The analyses of these subgroups will be exploratory in nature.

The treatment effects in subgroups will be estimated using stratified odds ratio for binary endpoints; and stratified HR for time to event endpoints. Stratification factors in the analysis model will include the randomization stratification factors as well as PD-L1 status at baseline (positive vs not positive). In the case of a subgroup analysis of one of the stratification factors, only the other two stratification factors will be included in the models. To evaluate the efficacy of talimogene laherparepvec in combination with pembrolizumab in subgroups defined by the stratification factors and key covariates, the treatment effect will be investigated using the Gail and Simon quantitative and qualitative interaction tests (1985). Post hoc power for a nominal 2-sided 5% significance level test

may be calculated to help aid in the assessment (see code fragment in [Appendix C](#)).

The adjusted hazard ratio of the treatment effect with the corresponding 95% confidence interval and p-value adjusting for each of the subgroup variables listed above, using the stratified Cox proportional hazards (PH) model, as well as adjusting for all subgroup variables simultaneously in a multiple regression analysis, will be presented.

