        os (in=b)
;
;
```

```
by usubjid;  
if a and b;  
run;
```

```
*** Inverse Probability Censoring Weighted Cox model ;  
proc phreg data=os_wgt;  
class armcd(ref='PB_PEM');  
model aval*cnsr(1)=armcd;  
strata <stratification factors>;  
freq weights / nottruncate;  
hazardratio armcd / alpha=0.05 cl=wald diff=ref;  
ods output hazardratios=hr_ci_ipcw;  
run;
```

C.14 Gail and Simon Quantitative and Qualitative Interaction Tests and Post Hoc Power Test

```
%macro int(ds      =, /* Dataset                               */
           txvar   =, /* Treatment indicator                   */
           sgroup  =, /* Subgroup variable                                         */
           time    =, /* Time to event variable                                    */
           censor  =, /* Censor var 1=observed 0=censored                         */
           covar   =, /* Covariates for model                                     */
           alpha   =, /* 2-sided nominal alpha for power                         */
           outf    =  /* SASname of results file                                 */ );

proc sort data=&ds out=&ds._d1;
  by &sgroup;
run;

/*
proc printto new print=&outf; run;
*/
ods output ParameterEstimates=phfit;
proc phreg data=&ds._d1;
  model &time*&censor(0)=&txvar &covar
  / rl ties=exact;
  by &sgroup;

data ph (keep=&sgroup estimate v rename=(estimate=b));
  set phfit (keep=&sgroup estimate stderr);
  v=stderr**2;

proc transpose data=ph prefix=b out=b (drop=_name_);
  var b;
proc transpose data=ph prefix=v out=v (drop=_name_);
  var v;

data t; merge b v;
  label H='(GS)|Quant.|Test|Value'
        ph='(GS)|Quant.|p-val' ph_p='(GS)|Quant.|Post Hoc|Power'
        Q='(GS)|Qual.|Test|Value' pq='(GS)|Qual.|p-val'
        pp='(PG)|Qual.|p-val' Qmin='(PG)|Qmin' Qmax='(PG)|Qmax'
        alpha='Alpha|2-tail';
  alpha = &alpha+0;
  array b b1-b30;
  array v v1-v30;
  g=0; do i=1 to 30; if b{i} ne . then g+1; end;

  * (GS) Quantitative interaction test ;
  n=0; d=0;
  do i=1 to g; n=n + b{i}/v{i}; d=d + 1/v{i}; end;
  Dbar=n/d;
  H=0;
  do i=1 to g; H=H + ((b{i}-Dbar)**2)/v{i}; end;
  ph=1-probchi(H,g-1);

[figure not shown]
  * Post hoc power ;
  c_alpha = quantile('CHISQ', 1-alpha, g-1);
  ph_p = 1 - probchi(c_alpha, g-1, H);

[figure not shown]
  * (GS) Qualitative Interaction ;
```

[figure not shown]
```
Q=0; Qn=0; Qp=0; pq=0;
do i=1 to g;
  Qn=Qn + ((b{i}**2)/v{i})*resolve(b{i}>0);
  Qp=Qp + ((b{i}**2)/v{i})*resolve(b{i}<0);
end;

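### The optional post hoc power for the quantitative interaction test restates its p-value, so it cannot tell a consistent effect from too few events

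*SAP*

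**What the plan says.** SAP 7.9 sets out how interaction is to be examined for the randomisation strata and for key covariates: "the treatment effect will be investigated using the Gail and Simon quantitative and qualitative interaction tests (1985"). It then permits an add-on, "Post hoc power for a nominal 2-sided 5% significance level test". The status of that add-on is that it "may be calculated to help aid in the assessment", and the reader is sent to Appendix C for the code. The same section calls these subgroup analyses exploratory.

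In Appendix C, item C.14, the quantitative test pools the subgroup log hazard ratios with inverse-variance weights and forms H, the weighted sum of squared deviations from the pooled value. Three lines then matter:

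- p-value: "ph=1-probchi(H,g-1")
- critical value: "c_alpha = quantile('CHISQ', 1-alpha, g-1")
- post hoc power: "ph_p = 1 - probchi(c_alpha, g-1, H")

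The third argument in the last line is the noncentrality, and it is the observed H. Neither 7.9 nor C.14 names an interaction size that the trial should be able to detect.

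Most factors listed in 7.9 have two levels. Two have three: "HSV-1 serostatus (positive vs negative vs missing/unknown") and baseline BRAF V600 mutation.

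**The concern.** A reader looks at power beside a non-significant interaction test to decide between two explanations: the effect is consistent across subgroups, or there were too few events to see a difference. An answer needs an interaction size fixed independently of the data, and the precision of the estimate. C.14 supplies neither. It substitutes the observed statistic for the true noncentrality, so the output depends only on how large H happened to be, which the p-value already conveys.

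What is at stake is interpretation. SAP 7.9 repeats the efficacy analyses over eleven listed factors, including PD-L1 status, disease stage, LDH and HSV-1 serostatus. For each non-significant interaction the number offered as an aid would be low by construction, and a well-powered null result would look much like a poorly powered one.

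**Working it through.** The documents give no numerical post hoc power, so there is no figure to reproduce. The check evaluates the C.14 formulas directly, with alpha = 0.05 from SAP 7.9.

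**Formulas.** With g subgroups, log hazard ratios b_i and variances v_i:

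- pooled value D = Σ(b_i/v_i) / Σ(1/v_i)
- H = Σ (b_i − D)² / v_i
- p = P(χ² with g−1 df > H)
- c = 95th percentile of χ² with g−1 df, which is 3.841 for g = 2 and 5.991 for g = 3
- printed power = P(noncentral χ² with g−1 df and noncentrality H > c)

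Once g is fixed, both p and the printed power are functions of H alone. One falls and the other rises as H grows, so each determines the other. Event counts do not enter separately.

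**By hand for two levels.** With 1 df, printed power = Φ(√H − 1.96) + Φ(−√H − 1.96).

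- At p = 0.05, H = 3.841 and √H = 1.96, so power = Φ(0) + Φ(−3.92) = 50.0%.
- At p = 0.30, H = 1.074 and √H = 1.036, so power = Φ(−0.924) + Φ(−2.996) = 17.9%.

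**Full evaluation.**

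| Interaction p-value | Printed power, 2 levels | Printed power, 3 levels |
|---|---|---|
| 0.05 | 50.0% | 58.3% |
| 0.10 | 37.6% | 47.0% |
| 0.20 | 24.9% | 34.2% |
| 0.30 | 17.9% | 26.5% |
| 0.50 | 10.4% | 16.8% |
| 0.90 | 5.2% | 6.6% |

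Printed power fell strictly with p over a fine grid, so the first row is the ceiling for any non-significant result. If the five-level individual disease stage in SAP 4.2 counted as a key covariate (4 df), its ceiling would be 69.0%.

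**Behaviour with no true interaction (simulation).** The printed value averages 17% for two levels and 22% for three, while the test rejects 5% of the time. Among non-significant two-level tests the median printed value is 9.7% and the maximum 50%, the same at 346 events as at 5000.

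**Behaviour when true power is 80% (two levels, simulation).** Among results that come out non-significant, the printed value averages 31%.

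**What an informative power looks like.** Inputs: 346 deaths (SAP 8.1.4, OS primary analysis); a ratio of subgroup hazard ratios of 1.5 and the split of deaths between two subgroups, both assumed because the documents give neither. The standard error of the log ratio is √(4/d₁ + 4/d₂), and power ≈ Φ(ln 1.5/SE − 1.96), with ln 1.5 = 0.405.

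| Assumed split | d₁, d₂ | SE | 95% CI factor, exp(1.96 × SE) | Power for ratio 1.5 |
|---|---|---|---|---|
| 50/50 | 173, 173 | 0.215 | 1.52 | 47% |
| 60/40 | 207.6, 138.4 | 0.219 | 1.54 | 46% |
| 80/20 | 276.8, 69.2 | 0.269 | 1.69 | 33% |
| 90/10 | 311.4, 34.6 | 0.358 | 2.02 | 20% |

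These values move with the split. The C.14 value at a given p does not.

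**The case against.** The strongest reply is that little hangs on this, and several stronger readings go further than the documents do.

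- **Interactions must be judged by post hoc power.** A reader might infer this, but SAP 7.9 only permits the calculation. The planned analysis is the Gail-Simon tests.
- **All the interaction tests are affected.** They are not. C.14 attaches power to H, the quantitative statistic. The qualitative tests in the same macro have none.
- **The plan labels null interactions as low power.** Nothing in 7.9 or C.14 sets a threshold, prints a label or gives a rule of interpretation. The misreading is foreseeable but not prescribed.
- **The printed power is always too high.** That is too general. It exceeds the true rejection rate when the interaction is absent, but for a two-level test with 80% true power its mean is about 72%.
- **Confirmatory conclusions are at risk.** They are not. None of these tests is among the five alpha-controlled hypotheses. The OS test excluding stage IVM1c is handled separately in the graphical procedure.

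Two further replies have partial force. First, power for moderate interactions really is modest here (at most 47% for a ratio of 1.5), so a reader who concludes that events were too few will often be right. But the printed number is no evidence for that, and it misleads for larger interactions: at an assumed 50/50 split, true power for a ratio of 0.50 is 90%. Second, SAP 7.9 already plans effect estimates within each subgroup, and SAP 10.5.1.1 gives 95% CIs for the full-set hazard ratios that 7.9 repeats. That covers precision within subgroups. No CI for the difference between subgroups is stated.

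Being optional and exploratory limits the harm but gives the quantity no use, and leaves room to cite it selectively once results are known.

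**Conclusion.** The point holds in this limited form and is minor. The post hoc power permitted by SAP 7.9, as coded in C.14 for the quantitative test, carries no information beyond the p-value. That follows from the code alone and needs no assumption about the data. The ceilings for non-significant results (50.0% and 58.3%) are exact evaluations at alpha 0.05; the averages with no interaction (17% and 22%) come from simulation. The power figures for a ratio of 1.5 are illustrative only: they concern OS at 346 deaths, rest on assumed splits and an assumed ratio, and use a normal approximation.

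**What to change.** In SAP 7.9, delete the post hoc power sentence. In C.14, delete the critical-value and post hoc power statements, the alpha macro parameter and its assignment, and the matching label and print entries.

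In their place, for each subgroup factor:

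- **Time-to-event endpoints:** report the ratio of subgroup hazard ratios with its 95% CI. For two levels this is exp(b₁ − b₂ ± 1.96·√(v₁ + v₂)), from quantities the macro already holds.
- **Three-level factors (HSV-1 serostatus, BRAF V600):** state a reference level and report two ratios, each with its CI.
- **Binary endpoints:** report the ratio of odds ratios with its 95% CI. C.14 fits only a Cox model, so this needs a short separate step.
- **Power, if wanted:** compute it for a ratio fixed before unblinding, from the event counts in each subgroup.

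The cost is one sentence, a handful of code lines and a small addition to the subgroup tables. No data collection, sample size, alpha allocation or analysis timing changes.

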8.1 Interim Analyses

A DLT interim safety analysis was planned and conducted for phase 1b. Data were reviewed by a DLRT.

All analyses prior to the primary OS analysis will be conducted by an external independent biostatistics group (IBG) and reviewed by the DMC per the DMC charter. The analyses will include safety monitoring, iORR/iDCR futility, primary and possibly interim PFS, and interim OS (including OS futility) analyses. The study team is responsible for conducting the primary analysis of OS and all subsequent analyses.

8.1.1 DLT Safety Analysis (Phase 1b)

An interim safety analysis in phase 1b to evaluate DLT included 6 subjects who were eligible for DLT evaluation. A DLRT consisting of the Amgen study team, including at least one clinician, safety representative, and biostatistician, at least one representative from the Merck study team, and at least one investigator participating in the study who recruited subjects into the phase 1b, was to review the safety data to evaluate possible DLTs. This team was to recommend either to enroll more subjects for DLT evaluation in the phase 1b, to prematurely stop enrollment into the phase 1b, or to declare that the combination is tolerable and open the phase 3. The DLRT would review additional safety data from subjects enrolled in the phase 1b beyond the 6 DLT evaluable subjects to further assess the overall safety profile of talimogene laherparepvec in combination with pembrolizumab.

8.1.2 Interim Safety Analysis (Phase 3)

An independent Data Monitoring Committee (DMC) will review interim safety analyses to evaluate the safety of talimogene laherparepvec in combination with pembrolizumab in the target population for the phase 3. The first two safety analyses occurred after approximately 20 and 100 total subjects had enrolled in phase 3, respectively, who had

the opportunity to be followed for at least 6 weeks after initiating study treatment. Additional safety review meetings may occur every 6 months after the interim iORR and iDCR futility review meeting (Section 8.1.3) until the primary analysis of OS. Unblinded safety tables and listings by treatment arm will be prepared for the DMC by IBG according to the DMC charter. All available safety data from the phase 1b part of the study was provided to DMC at the time of the first planned interim safety analysis (ie, at 20 subjects trigger) in phase 3.

8.1.3 Interim iORR and iDCR Futility Analysis (Phase 3)

An interim futility analysis of iORR and iDCR per BICR using modified irRC-RECIST is planned when approximately 160 subjects (ie, 80 per arm) have been enrolled and have had a chance to be followed for at least 24 weeks (+2 weeks). This interim futility analysis will be conducted by the DMC with support from an IBG. The analysis will be limited to those subjects who had the potential to be followed for at least 24 weeks (+ 2 weeks). All tumor response data will be included up to 26 weeks from the date of first dose of study therapy for the 160th enrolled subject (or randomization date if subject is not dosed).

Beta (8.75, 16.25) and Beta (12.5, 12.5) prior distributions are assumed for the true placebo plus pembrolizumab arm (arm 2) iORR and iDCR in the trial population with means equal to 0.35 and 0.50, respectively, and both with the precision equal to a sample size of 25. Beta (10.08, 10.92) and (14.91, 6.09) prior distributions are assumed for the iORR and iDCR for the combination of pembrolizumab and talimogene laherparepvec (arm 1) with means equal to 0.48 and 0.71, respectively, and both with a concentration parameter of 21. The priors for the combination correspond to the results from a 24-week minimum follow-up analysis of the 21 subjects in the phase 1b part of the study.

Beta posterior distributions for the iORR and iDCR will be calculated for each arm based on the corresponding prior distribution and the observed study iORR and iDCR results. The iORR futility criterion will be a posterior probability < 0.65 of at least a 6% absolute iORR increase (Arm 1 – Arm 2), and the iDCR futility criterion will be a posterior probability < 0.75 of at least a 10% absolute iDCR increase. The DMC will declare the combination therapy futile if both the iORR and iDCR futility criteria are met; however, the DMC's recommendation will be non-binding and therefore the sponsor will make the final decision to terminate the study prematurely.

8.1.4 Interim Efficacy and Futility Analysis (Phase 3)

There are **5** planned analysis time points for hypothesis testing, including primary and/or interim analyses of the 5 hypotheses (H): H₁, associated with OS; H₂, PFS by BICR assessed modified RECIST 1.1; H₃, iPFS by BICR assessed modified irRC-RECIST; H₄, iCRR by BICR assessed modified irRC-RECIST; and H₅, OS subgroup excluding IVM1c. The analysis times are defined by the following event-driven timepoints with the DMC responsible for Analyses **#1, #2, and #3**.

1. **OS interim analysis and PFS primary analysis at 407 PFS events (DMC).**
2. OS interim analysis at 282 events (including a futility analysis) (DMC).
3. **OS interim analysis at 315 events (DMC).**
4. OS primary analysis at 346 events.
5. OS subgroup primary analysis at earlier of 208 events in subgroup or 5 years minimum follow-up.

Note that there is no sequential order in these **5** analysis times (with the exception that Analysis #2 is before Analysis #3 and **Analysis #3 is before analysis #4**) and the analyses may be combined. Each analysis time may also include interim or primary analyses for the other endpoints. Endpoints to be analyzed, and the type of analysis (ie, interim or primary), are presented in [Table 3](#) and are dependent on which hypotheses have been rejected. For example, testing for iCRR and iPFS at an analysis timepoint will be conditional upon previously rejecting either H₁ or H₂. O'Brien-Fleming group sequential boundaries based on the Lan-DeMets approach ([O'Brien and Fleming, 1979](#)) will be used for testing endpoints with interim analyses. Multiple testing procedures will utilize the graphic-based Maurer-Bretz approach ([Section 10.5.1.1](#)).

The information fractions will be based on the **observed** events included at the time of analysis for testing of all time to event endpoint null hypotheses (ie, H₁, H₂, H₃, and H₅) and it will be based on the number of subjects with potential follow-up time of at least 36 weeks for testing the iCRR null hypothesis (ie, H₄). The maximum information for testing iCRR is all randomized subjects. Each analysis time will have a corresponding database snapshot; however, there will not be a separate snapshot for each endpoint tested at the same analysis time.

1. The initial alpha allocation for testing the hypothesis of PFS (H_2) is 0.5% and 4.5% for OS (H_1). There will not be a nominal alpha passed back to H_2 after rejecting H_1 or other hypotheses at any analysis.
2. An interim OS analysis will be performed at Analysis #1 with all **observed** death events, regardless if H_2 is rejected. In the event when Analysis #2 occurs prior to Analysis #1, then it will include an interim analysis to test H_2 for PFS (using all PFS events) and, if H_2 is not rejected, it will be tested again at the planned time for Analysis #1. However, if the projected time for achieving 407 PFS events is within 4 months from the projected 282 OS events time, then Analysis #2 will be combined with Analysis #1 and be performed at Analysis #1 using all death events with PFS times censored after the 407th PFS event.
3. At each of the **5** planned analysis times, it will be considered an interim analysis of iCRR and iPFS, rather than the primary analysis, if the maximum information has not been reached for the respective endpoint at that time. For example, if H_3 is tested in an analysis that includes fewer than 256 iPFS events, then it will be an interim analysis of iPFS that includes all observed events; otherwise, it will be the primary analysis with all iPFS times censored after the date of the 256th event. If all randomized subjects do not have at least 36 weeks follow-up in an analysis, then it will be an interim analysis for iCRR only including those subjects with at least 36 weeks follow-up; otherwise, it will be the primary analysis and include all randomized subjects. With the exception of PFS, the hypothesis for an endpoint may be re-tested after its primary analysis using its primary analysis data if alpha is subsequently propagated to it from the rejection of another hypothesis.
4. Assuming Analysis #1 is before Analysis #2, and at Analysis #1 the null hypothesis of PFS (H_2) is rejected, the hypotheses H_3 and H_4 will be tested. H_1 will be tested at Analysis #1 regardless of whether H_2 is rejected. The iPFS (H_3) and iCRR (H_4) can be tested if H_2 is not rejected but H_1 is significant. Likewise, OS subgroup (H_5) can be tested at Analysis #1 if any of the following set of hypotheses are rejected: (1) H_2 and H_3 ; (2) H_2 and H_4 ; (3) H_1 and H_3 ; or (4) H_1 and H_4 .
5. If projections indicate 256 iPFS events will occur in the same timeframe as either Analysis #1 or Analysis #2, then the option will be considered to extend the data cutoff to include all 256 iPFS events. In this event, Analysis #1 will have PFS times censored after the 407th PFS event and Analysis #1 or #2 will include all OS events.
6. The OS hypothesis (H_1) will be tested at Analyses #1-4 with all (Analysis #1) or required number (Analysis #2, Analysis #3, **and Analysis #4**) of events in the absence of its prior rejection (or futility at Analysis #2).
7. The OS subgroup hypothesis (H_5) will be tested at the first and all subsequent analysis times when alpha can be propagated to it from the rejection of H_1 or H_2 followed by H_3 and/or H_4 . All OS events in the subgroup at the end of 5 years follow-up will be used if 208 events have not been observed. If H_1 is not rejected by Analysis #4, it will be tested again using events at Analysis #4 if alpha can be propagated from the rejection of H_5 at Analysis #5.
8. Likewise, H_3 and H_4 may be re-tested if not rejected by their primary analysis using their respective primary analysis data if H_1 is subsequently rejected.

Table 3 illustrates possible hypothesis tests at the 5 planned analyses.

Table 3. Study Analyses and Possible Hypothesis Tests

Analysis	Timing	Hypothesis Tested (Analysis Type)				
		H ₁ (OS)	H ₂ (PFS)	H ₃ (iPFS)	H ₄ (iCRR)	H ₅ (OS subgroup)
#1	407 PFS events	(IA)	(PA)	If reject H ₁ or H ₂ (IA if < 256 events)	If reject H ₁ or H ₂ (IA if includes fewer than all randomized)	If reject H ₂ and either H ₃ or H ₄ , or reject H ₁ and either H ₃ or H ₄ (IA if < 208 events)
#2	282 OS events	(IA)	n/a (IA if Analysis #2 is performed first)	If reject H ₁ or H ₂ (PA on first 256 events)	If reject H ₁ or H ₂ (PA if includes all randomized)	If reject H ₂ and either H ₃ or H ₄ , or reject H ₁ and either H ₃ or H ₄ (IA if < 208 events)
#3	315 OS events	(IA)	n/a	If reject H ₁ or H ₂ (PA on first 256 events)	If reject H ₁ or H ₂ (PA if includes all randomized)	If reject H ₂ and either H ₃ or H ₄ , or reject H ₁ and either H ₃ or H ₄ (IA if < 208 events)
#4	346 OS events	(PA)	n/a	See Analysis #2 & #3 above	See Analysis #2 & #3 above	See Analysis #2 & #3 above
#5	Earlier of 208 OS events in subgroup or 5 years minimum follow-up	If reject H ₂ previously and H ₅ (PA at first 346 events)	n/a	See Analysis #2 & #3 above	See Analysis #2 & #3 above	See Analysis #2 & #3 above (PA)

iCRR = complete response rate (by modified irRC-RECIST); iPFS = progression free survival (by modified irRC-RECIST); H = hypothesis; IA = interim analysis; n/a = not applicable; OS = overall survival; PA = primary analysis; PFS = progression free survival

Futility Analysis for OS

At the 282 OS events interim analysis (ie, Analysis #2), if hypothesis H₁ is not rejected, then an OS futility analysis will be evaluated by the DMC. The interim OS futility

analysis will be non-binding and define futility as a conditional power < 10% assuming a constant treatment effect (Denne, 2001); the corresponding OS futility boundary is 0.89, assuming a constant HR = 0.70. OS futility will also be evaluated by the DMC considering a possible non-constant treatment effect that increases over time (eg, a 2 interval model with a cutpoint between 4 to 8 months and constant treatment effect in each interval, where the second interval has a larger effect than the first one). To limit the probability of futility < 0.02, the futility boundary for the observed HR at 282 OS events analysis will be 0.93. Guidelines for this possible late effect are provided in the DMC charter amendment. Operating characteristics of the primary analysis of PFS and sequential tests of OS are shown in Table 4 based on the OS events expected at Analysis #1.

Table 4. Analysis Timing, Nominal Significance Levels, and Boundary Properties

Analysis	Data cut-off (mon)	Endpoint (scenario)	Event (% goal)	Efficacy nominal 2-sided α	Futile HR ^b	Prob. Futile ^b		Power total
						H ₀	H ₁	
PFS PA	44	PFS	407 (100)	0.0050				90%
OS IA ₁	44	OS (PFS-)	252 (73) ^a	0.0150				66%
		OS (PFS+)		0.0173				67%
OS IA ₂	52	OS (PFS-)	282 (82)	0.0187	0.89	84%	2%	76%
		OS (PFS+)		0.0212	0.89	83%	2%	77%
OS IA ₃	61	OS (PFS-)	315 (91)	0.0261				84%
		OS (PFS+)		0.0292				85%
OS PA	75	OS (PFS-)	346 (100)	0.0336				90%
		OS (PFS+)		0.0372				90%

IA = interim analysis; H₀ = null hypothesis; H₁ = alternative hypothesis; HR = hazard ratio; OS = overall survival; PFS = progression free survival; PA = primary analysis.

O'Brien-Fleming spending α for OS; futility if conditional power < 10%; H₀: HR = 1 and H₁: HR = 0.67 (PFS) and 0.70 (OS). Testing OS at an overall 2-sided 0.045 if PFS is not significant at 2-sided 0.005 (eg, PFS-); testing OS at 0.05 when all other null hypotheses are rejected (eg, PFS+).

^a The events for OS IA₁ are not pre-determined.

[figure not shown]
^b The futile HR and probabilities are shown for the conditional power criterion only which assumes a constant OS effect.

9. Data Screening and Acceptance

